^f Haematology will include a complete blood cell count [white blood cell count, haemoglobin (Hb), haematocrit, reticulocyte, and platelet count] and differential leukocyte count, including both percent and an absolute number of lymphocytes. Haematology need not be repeated on Cycle 1 Day 1 if screening haematology was within 5 days

^g Biochemistry will include albumin, Total bilirubin, Total protein, Alkaline Phosphatase (ALP), Alanine Aminotransferase (ALT, SGPT), Aspartate Aminotransferase (AST, SGOT), Gamma-glutamyl transferase (GGT), Lactate Dehydrogenase (LDH), Lipase, Amylase, Blood Glucose, Magnesium, Potassium, Bicarbonate, Sodium, Calcium, Chloride, Creatinine (creatinine clearance), Urea or Blood Urea Nitrogen (BUN), Haptoglobin, b2-microglobulin. Serum biochemistry need not be repeated on Cycle 1 Day 1 if screening chemistry was within 5 days.

^h Urinalysis: pH, ketones, specific gravity, bilirubin, protein, blood, and glucose.

ⁱ A urine pregnancy test will be conducted in all females of child bearing potential at the time of screening and during the study (treatment phase)

^j Chest X-ray will be done as a symptom directed investigation. Patients with signs and symptoms of Pneumonia will be allowed to go for chest X-ray investigation.

^k CT or MRI scans will be performed prior to the first study medication administration (dosing). CT or MRI scans are applicable for the patients with lymphadenopathy or organomegaly. Patients with abnormalities of blood parameters without any lymphadenopathy or organomegaly will not undergo CT or MRI scans. Patients who will be undergoing CT, should have baseline and every 3-months reports

Note: CMV, HIV, and Hepatitis serology testing will be conducted at the screening.

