1.2 Synopsis

Protocol Title: A prospective, multi-centre, phase IV clinical trial to assess the safety and efficacy of Acalabrutinib capsules in Indian adult patients with chronic lymphocytic leukaemia and relapsed and refractory mantle cell lymphoma

Version: 1.0 Date: 01 Sep 2020

Study sites and number of patients planned

No. of total screened patients: Approximately 150

No. of total enrolled patients: Approximately 100

No. of study sites: 10

Total planned study period	
Estimated date of the first patient in	Q4 2020
Estimated date of the last patient in	Q2 2021
Estimated date of last patient last visit	Q4 2021
Estimated date of database lock	Q2 2022
Clinical study report	Q3 2022

Rationale

Chronic lymphocytic leukaemia (CLL) is a malignancy of B cells that predominantly affects an elderly population. It is the most prevalent form of adult leukaemia, with an age-adjusted incidence of 3.3–6.4 per 100,000 person-years and a median age at diagnosis of 70 years (Noone AM, April 2018). The diagnosis of CLL is established using peripheral blood and immunophenotyping and requires the presence of a minimum of $5 \times 10^9/L$ monoclonal B cells that co-express the surface antigens CD5, CD19, CD20, and CD23. In routine practice, patients with asymptomatic early-stage disease should be monitored without therapy unless they have evidence of disease progression or disease-related symptoms. Treatment of CLL is initiated once there is evidence of progressive or symptomatic/active disease as defined by iwCLL guidelines (Hallek et al., 2018; Hallek et al., 2008). Despite the relatively long life expectancy for early-stage disease, CLL remains an incurable disease.

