Two cohorts of patients will be included in the current study (a) patients with CLL/SLL who are treatment naïve or have received at least one prior therapy (N= 90) and (b) patients with MCL

who have received at least one prior therapy (N= 10). Potential patients will undergo screening phase within 07 days prior to the first dose. Patients who meet the protocol-defined inclusion/exclusion criteria will be prospectively enrolled in the study.

Acalabrutinib capsules 100 mg are administered twice daily (BID) for 06 cycles, starting from Cycle 1, Day 1, and continuing up to Cycle 6, Day 28; or until study drug discontinuation due to either disease progression or, unacceptable toxicity, or other reasons, whichever occurs earlier.

Acalabrutinib will be provided by the Sponsor to patients in the Treatment Phase. The Sponsor shall also conduct laboratory investigations for safety and efficacy evaluations, including haematology, biochemistry, radiology, and electrocardiography (ECG), as mentioned in the SoA table.

Patient Population

Inclusion criteria

Patients are eligible to be included in the study only if all of the following inclusion criteria and none of the exclusion criteria apply:

1. Men and Women aged 18yrs or more.
2. Eastern Cooperative Oncology Group (ECOG) performance status of 0,1, or 2
3. Able to receive all outpatient treatments, all laboratory monitoring, and all radiologic evaluations.
4. The following laboratory parameters:
 - a. Absolute neutrophil count (ANC) ≥ 750 cells/ μ L or ≥ 500 cells/ μ L in patients with documented bone marrow involvement, and independent of growth factor support 07 days before the assessment
 - b. Platelet count $\geq 50,000$ cells/ μ L or $\geq 30,000$ cells/ μ L in patients with documented bone marrow involvement, and without transfusion support 07 days before the assessment
 - c. Aspartate transaminase (AST) and Alanine transaminase (ALT) ≤ 2.0 x ULN
 - d. Total bilirubin ≤ 1.5 x ULN
 - e. Estimated creatinine clearance of ≥ 30 mL/min
5. Refractory disease defined as achieving less than partial response with the most recent treatment within 6 months before study entry
6. Provision of signed, written and dated informed consent prior to any study-specific Procedures
7. The patients of either CLL or MCL:
 - a. **CLL patients:**
 - i. Treatment naïve or ≥ 1 prior systemic therapy for CLL
 - ii. Diagnosis of CD20+ CLL that meets published diagnostic criteria (Hallek et al. 2018)

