8.1.2 Safety assessments

Safety evaluations will include clinical laboratory parameters (haematology and biochemistry), physical examinations, vital sign measurements, ECG monitoring, ECOG performance status, adverse event monitoring, and death, as observed by the Investigator. Based on the previous *in vitro* studies, animal toxicological findings, and human studies with Acalabrutinib, arrhythmias (which includes atrial fibrillation), anaemia, hypertension, bleeding, infections, and second primary malignancies will be closely monitored. Any of the safety monitoring assessments may be performed more frequently, and adverse events should be evaluated by the Investigator according to the standard practice if clinically indicated.

Clinical safety laboratory assessments

The list of clinical safety laboratory tests to be performed are provided in Table 6 and Table 7. All protocol-required laboratory assessments, as defined in the table, must be conducted in accordance with the laboratory manual and the timing and frequency outlined in the SoA.

The Investigator should assess the available results with regard to clinically relevant abnormalities. The laboratory results should be signed, dated, and retained at the site as source data for laboratory variables.

For information on how AEs based on laboratory tests should be recorded and reported, refer Section 8.2.7.

Additional safety samples may be collected if clinically indicated at the discretion of the Investigator. The date, time of collection, and results (values, units, and reference ranges) should be appropriately recorded in the eCRF.

The haematology (Table 6), clinical chemistry (Table 7) and urinalysis (routine and microscopy) measurements will be performed at a local laboratory at or near the Investigator site.

A complete blood cell count will be conducted as per SoA (Table 1). It includes white blood cell count, haemoglobin, haematocrit, reticulocyte, platelet count and differential leukocyte count, including both percent and an absolute number of lymphocytes.

Table 6: Haematology

Haematocrit
Haemoglobin
Basophils
Eosinophils
Monocytes
Lymphocytes
Reticulocytes
Absolute Neutrophil Count
Platelet count
Total leucocyte count

Table 7: Clinical chemistry (serum or plasma)

Albumin
Glucose
Amylase
Lipase
Alkaline phosphatase
Lactate dehydrogenase
Alanine aminotransferase
Aspartate aminotransferase
Potassium
Bicarbonate
Sodium
Calcium
Total bilirubin
Chloride
Total protein

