Creatinine (creatinine clearance)
Urea or Blood Urea Nitrogen, depending on local practice
Gamma-glutamyl transferase
Magnesium
Haptoglobin
b2-microglobulin

Note: CMV serology, HIV (anti-HIV1 Ab, anti-HIV2 Ab), Hepatitis serology testing will be conducted at the screening that includes hepatitis B surface antigen (HBsAg), hepatitis B surface antibody (HBsAb), anti-HBc, and HCV antibody.

The local GLP certified laboratory will perform haematology and clinical chemistry tests. Additional analyses may be performed if clinically indicated.

Any clinically significant abnormal laboratory values should be repeated as clinically indicated and recorded in the eCRF.

All patients who have any Common Toxicity Criteria (CTC) Grade 3 or 4 laboratory values at the time of completion or discontinuation from study must have further tests performed until the laboratory values have returned to CTC Grade 1 or 2, unless these values are not likely to improve because of the underlying disease.

Urine Pregnancy Test

Urine pregnancy tests will be required only for women of childbearing potential. Urine pregnancy tests will be performed at Screening; on Cycle 1 Day 1; on Day 28 of Cycles 1-6; and at the early termination or End of study visit.

Physical examinations

For timing of individual measurements refer to the schedule outlined in (Table 1).

A complete physical examination will be performed and will include an assessment of the following (as clinically indicated): general appearance, respiratory, cardiovascular, abdomen, skin, head, neck (including ears, eyes, nose, and throat), lymph nodes, thyroid, musculoskeletal (including spine and extremities), and genital/rectal and neurological systems.

Symptom-directed physical exams, including tumour assessments by palpation, will be done during the treatment period and at the EOT visit.

Lymph nodes: The bi-dimensional diameters of the largest palpable lymph node/s in each of the following sites should be recorded: cervical, axillary, and inguinal. The dimensions of the liver and spleen below their respective costal margins, as assessed by palpation, should also be recorded.

Performance status will be assessed using ECOG performance status.

Vital signs

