#### 6.3.1 Primary Endpoint Analysis

Primary Endpoint evaluations will include adverse event monitoring, physical examinations, ECG monitoring, clinical laboratory investigations (haematology and biochemistry), vital sign measurements, ECOG performance status and death as observed by the Investigator.

Adverse Events (AEs), Serious Adverse Events (SAEs), and AEs of Special Interest (AESI) will be summarized using frequencies and percentages.

Physical examination will be collected as per visit scheduled. Physical examination results (normal /abnormal) from scheduled visits will be summarized for each body system. A listing will be provided for the Normal/abnormal physical examination parameters.

A 12-lead electrocardiogram (ECG) will be performed as per visit scheduled. ECG results (normal, abnormal clinically insignificant, abnormal clinically significant) will be summarized as counts and percentage.

Laboratory investigations (haematology and biochemistry) data will be collected as per visit scheduled. Laboratory values will be presented using the International System of Units (SI units). Observed values will be summarized descriptively (n, mean, median, standard deviation, minimum, and maximum values). A listing will be provided which contains data for each laboratory parameter.

Document Title:	Document ID:	BP04-01
Statistical Analysis Plan	Version Number:	3.1
	Effective Date:	25-Nov-2021

Vital signs will be performed as per visit scheduled. Vital signs parameters include Systolic Blood Pressure, Diastolic Blood Pressure, Heart Rate, Respiratory rate and Temperature. Descriptive summaries (n, mean, median, standard deviation, minimum and maximum values) of observed values in each vital sign parameter at each assessment visit will be presented. A listing will be provided for all vital signs parameters assessments.

ECOG will be performed as per visit scheduled. ECOG performance status will be summarized as counts and percentage.

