**Table 14.3.4.2. Summary of Laboratory assessment for Biochemistry**

	CLL/SLL (N=xx)	MCL (N=xx)	Total (N=xx)
Visit x			
Sample Collected			
Yes	xx (xx.xx)	xx (xx.xx)	xx (xx.xx)
No	xx (xx.xx)	xx (xx.xx)	xx (xx.xx)
Biochemistry Parameter x			
n	xx	xx	xx
Missing	xx	xx	xx
Mean (SD)	xx.x (xx.xx)	xx.x (xx.xx)	xx.x (xx.xx)
Median	xx.x	xx.x	xx.x
(min, max)	(xx.xx, xx.xx)	(xx.xx, xx.xx)	(xx.xx, xx.xx)

- The Capital "N" in the column header represents the total number Full Analysis Set.
- The small "n" in summary statistics represents the total number of Patients.
- SD = Standard Deviation, min=minimum, max=maximum
- Percentages in the "Sample collected" rows are based on number of patient in each group.
- Programmer Note: Generate summaries for the following parameters x – Albumin (g/dL), Glucose (mg/dL), Amylase (U/L), Lipase (U/L), Alkaline phosphatase (U/L), Lactate dehydrogenase (U/L), Alanine aminotransferase (U/L), Aspartate aminotransferase (U/L), Potassium (mmol/L), Bicarbonate (mmol/L), Sodium (mmol/L), Calcium (mg/dL), Total bilirubin (mg/dL), Chloride(mmol/L), Total Protein (g/dL), Creatinine (mL/min/1.73m^2), Urea (mg/dL), Blood Urea Nitrogen (mg/dL), Gamma-glutamyltransferase (U/L), Magnesium (mg/dL), Haptoglobin (g/L) and b2-microglobulin(ng/ML).
- Programmer Note Visit x: Visit 1 up to Visit 8.
- Source :Listing 16.2.15.2

Document Title:	Document ID:	BP04-01
Statistical Analysis Plan	Version Number:	3.1
	Effective Date:	25-Nov-2021

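### The SAP summarises AST, ALT and total bilirubin only as pooled raw values from local laboratories, so it cannot count patients with an elevation relative to their laboratory's upper limit of normal

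*Protocol*

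**What the plan says.** **Entry.** Criterion 4 (protocol Synopsis and Section 5.1, repeated in SAP 2.2.2) requires "Aspartate transaminase (AST) and Alanine transaminase (ALT) ≤ 2.0 x ULN" and "Total bilirubin ≤ 1.5 x ULN".

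**Measurement.** The Synopsis plans for "No. of study sites: 10". Protocol 8.1.2 states that haematology, chemistry and urinalysis "measurements will be performed at a local laboratory at or near the Investigator site", and later that "The local GLP certified laboratory will perform haematology and clinical chemistry tests". No central laboratory is named.

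**AE recording.** Protocol 8.2.7 says the CSR will summarise mandated laboratory results. On that basis it limits AE reporting of a deterioration to two cases: an SAE criterion is met, or the change is why treatment was stopped. Where symptoms accompany the change, the symptom is the AE.

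**Analysis.** SAP 6.3.1 places biochemistry among the primary endpoint evaluations. The method is: "Observed values will be summarized descriptively (n, mean, median, standard deviation, minimum, and maximum values"). Table 14.3.4.2 applies this at Visits 1 to 8 for CLL/SLL, MCL and Total, with "Alanine aminotransferase (U/L), Aspartate aminotransferase (U/L") and bilirubin in mg/dL. Listing 16.2.15.2 has columns for result, unit and finding, but none for a reference range.

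**The concern.** A transaminase value in U/L has to be read against the reference range of the laboratory that produced it. The protocol does this at entry and the SAP does not do it in the analysis. The table as planned gives location, spread and extremes of raw values, but not the number of patients whose liver tests rose.

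This matters because 8.2.7 sends one class of event to the laboratory summary on purpose: an elevation that is not serious, causes no symptoms and does not end treatment. If that summary cannot count such patients, no other planned table can. Safety is the primary objective, so the number is one that a reader of the CSR would expect to find.

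**Working it through.** **The plan's own figures.** The only computed design figures are the exact intervals in protocol Table 8: lower limit Beta(0.025; x, n−x+1), upper limit Beta(0.975; x+1, n−x). For n = 100 these give 0.00% to 3.62% at x = 0 and 4.90% to 17.62% at x = 10. All 43 filled cells reproduce to within 0.01 percentage point. They are not in dispute and serve below only to show precision.

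**Step 1: follow one ALT result through the documents.**

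| Stage | Place | Scale used |
|---|---|---|
| Entry | Protocol criterion 4c | Multiple of ULN |
| Repeat testing at completion or discontinuation | Protocol 8.1.2 | CTC Grade 3 or 4 |
| AE recording | Protocol 8.2.7 | Only if serious or the reason for stopping; otherwise any accompanying symptom |
| Summary | SAP 6.3.1, Table 14.3.4.2 | Raw U/L |
| Listing | SAP Listing 16.2.15.2 | Result and unit, without range |

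Both scales that the protocol applies to laboratory values, multiples of ULN and CTC grade, are absent from the SAP's laboratory outputs.

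**Step 2: what a raw value means.** Assumption: local ALT ULN lies between 35 and 55 U/L. The documents give no value.

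- Entry limit: 2.0 × 35 = 70 U/L at one end; 2.0 × 55 = 110 U/L at the other.
- A result of 90 U/L: 90/35 = 2.57 × ULN, or 90/55 = 1.64 × ULN. It is above the entry limit in one laboratory and within it in the other, and the pooled table treats the two alike.

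**Step 3: can the planned statistics give the count?** Take a hypothetical visit with 100 patients: 90 at 25 U/L, and ten at 90, 90, 95, 100, 100, 105, 105, 108, 108 and 110 U/L (sum 1,011).

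- Mean = (90 × 25 + 1,011)/100 = 3,261/100 = 32.6. The SD is 23.1, the median 25.0 and the maximum 110.
- These statistics are the same whatever the ULN. The count above 2 × ULN is not:

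| Assumed ULN (U/L) | 2 × ULN (U/L) | Patients above |
|---|---|---|
| 35 | 70 | 10 |
| 45 | 90 | 8 |
| 55 | 110 | 0 |

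Even with one common ULN, the maximum would show only whether at least one patient exceeded the limit, not how many. With ULNs from 35 to 55 it does not show even that: 110 U/L is 110/35 = 3.14 × ULN or 110/55 = 2.00 × ULN.

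**Step 4: what a count would add.** A count of patients takes the exact interval the protocol already plans for key proportions. With 100 patients, 3 above a limit is 3.0% (0.62% to 8.52%) and 10 is 10.0% (4.90% to 17.62%). Visit-by-visit counts cannot be added up, since one patient may be high at several visits. A patient-level incidence therefore needs the worst post-baseline value.

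**The case against.** Several points on the other side stand.

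- **2.0 × ULN is an entry limit, not a toxicity threshold.** A reader might infer that the protocol judges liver toxicity on that scale. It does not: 8.1.2 and Appendix B use CTC/CTCAE grades. The entry limits are useful as a reference point, but the counts should include grades.
- **Serious liver events are not lost.** A reader might infer that liver toxicity as a whole disappears from the report. Events that are serious or end treatment are recorded as AEs, and symptoms accompanying a laboratory change are AEs too. Liver toxicity is not a named AE of special interest.
- **The spread of local ULNs is unknown.** Local testing makes differences plausible, but the documents do not state them. That pooled means are materially distorted, or move when one site's patients leave, is not shown.
- **Some local reading may already be captured.** Protocol 8.1.2 has the investigator assess results for clinical relevance, and the biochemistry listing has a finding column, possibly a normal/abnormal call. Its content is not defined there, and Table 14.3.4.2 does not use it.
- **Only AST, ALT and bilirubin have ULN criteria.** The argument does not reach ALP, GGT, LDH, amylase or lipase.
- **The study is descriptive.** Without hypothesis tests, no inference fails. That limits the weight of the point, but describing safety is the purpose of the study.

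The central gap remains: the SAP plans no count of elevations on any scale.

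**Conclusion.** The point holds for AST, ALT and total bilirubin. As planned, the laboratory summary cannot say how many patients had an elevation relative to their laboratory's ULN, and 8.2.7 makes that summary the main place for elevations that are non-serious, without symptoms and not a cause of stopping. The conclusion that the count cannot be recovered from the planned statistics does not depend on how much ULNs vary. The size of the illustration does: under the assumed 35 to 55 U/L range the entry limit moves between 70 and 110 U/L, and the same hypothetical summary fits 10, 8 or 0 patients above it. The limitation is in the planned table. The count could still be produced if the ranges are in the database. It is worth correcting because the change is cheap and serves the primary objective.

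**What to change.** In SAP 6.3.1 and Table 14.3.4.2:

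1. Report AST, ALT and total bilirubin as multiples of the reporting laboratory's ULN. The ratio has no unit, so it also avoids the mismatch between the SI units promised in 6.3.1 and the mg/dL shown for bilirubin in the table.
2. Add counts and percentages, by visit and for the worst post-baseline value, above the entry limits (AST or ALT > 2.0 × ULN, bilirubin > 1.5 × ULN) and by CTCAE grade. State one CTCAE version for this table: Appendix B cites 5.0 or above and Appendix C cites 4.03, and the sponsor needs to reconcile them.
3. Add the ULN to Listing 16.2.15.2.

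**Cost.** SAP wording, some extra programming and no new patient procedure. One thing must be confirmed first: that local reference ranges are collected for routine samples. Sites need the ULN to apply criterion 4, but the sentence in protocol 8.1.2 on recording ranges in the eCRF follows the one on additional samples, so routine capture is not certain.

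**Optional and minor.** The Schedule of Activities allows "Urea or Blood Urea Nitrogen (BUN"), and the SAP gives each its own row in mg/dL, so neither row need cover all patients. Converting BUN to urea (60.06/28.01 = 2.14) would give one row for all. Normalising the other enzymes is not needed for this point.

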Patients who are observed to receive clinical benefit from Acalabrutinib after completion of treatment phase, may continue to receive Acalabrutinib, if in the opinion of their treating physician they are continuing to derive clinical benefit from continued treatment or have not progressed clinically. The patients may continue treatment via drug supply (provided by AstraZeneca) until disease progression or withdraw of drug due to side effects or investigators decision whichever comes first.

These subjects shall receive the study drug free of cost in case if there is no coverage / reimbursement through a separate patient support program and will not receive the medication via the clinical trial supply for this study. These subjects shall not be actively monitored for AE's and it will be the responsibility of the treating physician to ensure reporting of all SAE's,

pregnancies, overdose and medication errors to the relevant authorities as per the standard spontaneous safety reporting practice in India.

Safety Evaluations

Safety evaluations will include adverse event monitoring, physical examinations, ECG monitoring, clinical laboratory investigations (haematology and biochemistry), vital sign measurements, ECOG performance status, and death as observed by the Investigator. Based on previous *in vitro* studies, animal toxicological findings, and human studies with Acalabrutinib, arrhythmias (which includes atrial fibrillation), anaemia, hypertension, bleeding, infections, and second primary malignancies will be closely monitored. Any of the safety monitoring assessments may be performed more frequently, and adverse events should be evaluated by the Investigator according to the standard practice if clinically indicated.

Efficacy Evaluations

All patients who receive Acalabrutinib capsule 100 mg BID will be evaluated for efficacy once every 03 months during the treatment phase. Efficacy will be assessed based on iwCLL 2018 criteria for CLL/SLL (Hallek et al., 2018) and for MCL (Cheson et al., 2014). Efficacy will be based on objective response [Complete Remission (CR) + Partial Remission (PR) and partial response with lymphocytosis (PRL)] via Computed Tomography (CT) scans or Magnetic Resonance Imaging (MRI).

Statistical methods:

Sample Size Justification

The primary endpoint of the trial is to demonstrate the safety profile of Acalabrutinib in routine clinical practice as assessed by the incidence of adverse events (AEs) (Serious and Non-serious AEs) observed during the trial. As per the Health Authority requirement, the total sample size of the study will be approximately 100.

Hypothesis

No formal hypothesis testing will be conducted.

[figure not shown]
Statistical Analysis

Categorical data will be summarized using frequencies and percentages. Continuous data will be summarized with descriptive statistics, including mean, standard deviation, median, minimum, and maximum. Confidence intervals will be supplied for key proportions (including objective response rate) using the Clopper-Pearson method.

